5.2. Number of Participants

Up to 60 subjects may be enrolled so that approximately 36 to 48 subjects complete the study.

5.3. End of Study Definition

End of the study is the date of the last visit or last scheduled procedure shown in the Schedule of Activities (Section 2) for the last subject.

5.4. Scientific Rationale for Study Design

This is a single-site, subject- and investigator-blind, randomized, placebo-controlled, SD and MD study in healthy Japanese and Caucasian subjects. This study is conducted to support the inclusion of Japanese subjects in future studies involving LY3337641. Healthy Caucasian subjects are also included in this study for assessment of both healthy Japanese and Caucasian subjects. The number of subjects in this study is deemed sufficient for the safety, tolerability, and PK data that will be assessed in both Japanese and Caucasian subjects. Intensive assessment of electrocardiograms (ECGs) will be done in this study, since thorough ECG data have not been obtained so far. The study will be subject and investigator blind, with the subjects, investigators, and site staff unaware of actual treatment (LY3337641 or placebo) but aware of dose level

assigned to the cohort. This design is being used to minimize bias in safety and tolerability assessments.

5.5. Justification for Dose

CCI [REDACTED]

[REDACTED]

[REDACTED]

[REDACTED]

6. Study Population

Eligibility of subjects for study enrollment will be based on the results of screening medical history, physical examination, vital signs, clinical laboratory tests, and ECG.

A chest x-ray will be completed at screening unless one has been obtained within the past 12 months, and the x-ray and/or report are available for review.

The nature of any conditions present at the time of the physical examination and any preexisting conditions will be documented.

Screening may occur up to 28 days prior to Day 1. Subjects who are not enrolled within 28 days of screening may be subjected to an additional medical assessment and/or clinical measurements to confirm their eligibility.

Prospective approval of protocol deviations to recruitment and enrollment criteria, also known as protocol waivers or exemptions, are not permitted.

6.1. Inclusion Criteria

Subjects are eligible for inclusion in the study only if they meet all of the following criteria at screening and/or enrollment:

[1] are overtly healthy males and females, as determined by medical history and physical examination

[1a] male subjects:

agree to use an effective method of contraception (barrier contraceptives, such as latex condoms, or complete abstinence from sexual intercourse with women) for the duration of the study and 3 months following the last dose of IP

[1b] female subjects:

women of childbearing potential may participate and include those who test negative for pregnancy prior to initiation of treatment (as indicated by a negative serum pregnancy test at the screening visit followed by a negative urine pregnancy test within 24 hours prior to exposure) and agree to remain abstinent or use either 1 highly effective method of contraception (such as combination oral contraceptive, implanted contraceptive, or intrauterine device) or a combination of 2 effective methods of contraception (such as male or female condom with spermicide, diaphragm with spermicide, or cervical sponge) during the study and for 4 weeks following the last dose of the IP

women not of childbearing potential may participate and include those who are:

- A. infertile due to surgical sterilization (hysterectomy, bilateral oophorectomy, or tubal ligation) performed at least 6 months prior to dosing or congenital anomaly such as müllerian agenesis or
- B. postmenopausal, defined as either
 - i. A woman aged 50 years or older who has an intact uterus, is not on hormone therapy, and has had either
 - a) cessation of menses for at least 1 year or
 - b) 6 to 12 months of spontaneous amenorrhea with a follicle-stimulating hormone >40 mIU/mL or
 - ii. A woman aged 55 years or older who is not on hormone therapy and has had at least 6 months of spontaneous amenorrhea or
 - iii. A woman aged 55 years or older with a diagnosis of menopause prior to starting hormone replacement therapy
- [2] are aged 20 to 64 years, inclusive, at screening
- [3] have a body mass index of 18.0 to 32.0 kg/m², inclusive, at screening
- [4] have clinical laboratory test results within normal reference range for the population or investigative site or results with acceptable deviations that are judged to be not clinically significant by the investigator
- [5] have venous access sufficient to allow for blood sampling as per the protocol
- [6] are reliable and willing to make themselves available for the duration of the study and are willing to follow study procedures
- [7] are able and willing to give signed informed consent
- [37] are 1st generation Japanese or Caucasian.
To qualify as a subject of 1st generation Japanese origin, the subject, the subject's biological parents, and all of the subject's biological grandparents must be of exclusive Japanese descent and born in Japan.

6.2. Exclusion Criteria

Subjects will be excluded from study enrollment if they meet any of the following criteria at screening and/or enrollment:

- [8] are investigative site personnel directly affiliated with this study and their immediate families. Immediate family is defined as a spouse, biological or legal guardian, child, or sibling
- [9] are Lilly or Covance employees

- [10] are currently enrolled in a clinical trial involving an IP or off-label use of a drug or device or are concurrently enrolled in any other type of medical research judged not to be scientifically or medically compatible with this study
- [11] have participated, within the last 30 days, in a clinical trial involving an IP. If the previous IP has a long half-life, 3 months or 5 half-lives (whichever is longer, if known) should have passed
- [12] have previously completed or withdrawn from this study or any other study investigating LY3337641 and have previously received the IP
- [13] have known allergies to LY3337641, related compounds or any components of the formulation, or history of significant atopy
- [14] have an abnormality in the 12-lead ECG that, in the opinion of the investigator, increases the risks associated with participating in the study or affects or confounds the QTc analysis (the ECG waveform morphology or rhythm are incompatible with reliable measurement of ECG intervals) or have Fridericia-corrected QT interval (QTcF) >450 msec for males and >470 msec for females
- [15] have an abnormal blood pressure or pulse rate (supine) as determined by the investigator
- [16] have a significant history of or current cardiovascular, respiratory, hepatic, renal, gastrointestinal (cholecystectomy not acceptable), endocrine, hematologic, dermatologic, or neurologic disorders capable of significantly altering the absorption, metabolism, or elimination of drugs; of constituting a risk when taking the IP; or of interfering with the interpretation of data
- [17] have known or ongoing psychiatric disorders
- [18] regularly use known drugs of abuse and/or show positive findings on urinary drug screening
- [19] show evidence of human immunodeficiency virus (HIV) infection and/or positive human HIV antibodies
- [20] show evidence of hepatitis C and/or positive hepatitis C antibody
- [21] show evidence of hepatitis B and/or positive hepatitis B surface antigen (HBsAg)
- [22] are positive for hepatitis B core antibody (HBcAb+)
- [23] are women who are lactating
- [24] have used or intend to use over-the-counter or prescription medication, including herbal medications, within 14 days prior to dosing
- [25] have donated blood of more than 500 mL within the month prior to screening

- [26] have an average weekly alcohol intake that exceeds 21 units per week and are unwilling to follow instructions in Section 6.3.2 (1 unit = 12 ounces or 360 mL of beer, 5 ounces or 150 mL of wine, and 1.5 ounces or 45 mL of distilled spirits)
- [27] are subjects whose tobacco consumption is more than 10 cigarettes per day or the equivalent or subjects who are not willing to refrain from smoking for 48 hours prior to clinical research unit (CRU) admission and during CRU stay
- [28] have a history of, in the opinion of the investigator, excessive methylxanthine use within the previous 3 months or are unwilling to abide by restrictions as specified in Section 6.3.2. Excessive intake is defined as more than 6 units of caffeine per day; 1 caffeine unit is contained in the following items: 1 (177 mL) cup of coffee, 1 (355 mL) cup of tea, 2 (355 mL) cans of cola, or 3 ounces (85 g) of chocolate
- [29] have had symptomatic herpes zoster within 3 months of screening, as determined by clinical history
- [30] have active or latent tuberculosis (TB) based on a positive medical history, examination, and/or TB test results. QuantiFERON®-TB Gold Plus test (QFT-Plus or equivalent) will be used for TB testing, and subjects must test negative to participate
- [31] have a screening chest x-ray with evidence of medically significant disease, such as malignancy, infection, pulmonary disease, or cardiac failure
- [32] have received live vaccine(s) within 1 month of screening or intend to during the study
- [33] are immunocompromised
- [34] in the opinion of the investigator or sponsor, are unsuitable for inclusion in the study
- [35] have had exposure to significant diagnostic, therapeutic, or employment-related radiation within 12 months prior to dosing (eg, serial x-ray or computed tomography scans, barium meal, current employment in a job requiring radiation exposure monitoring)
- [36] have a history of constipation or have had acute constipation within 3 weeks prior to admission

6.3. Lifestyle and/or Dietary Requirements

Throughout the study, subjects may undergo medical assessments and review of compliance with requirements before continuing in the study.

6.3.1. Meals and Dietary Restrictions

Before each morning dose in the SD and the MD cohorts, subjects will be fasted overnight for at least 10 hours following a light supper on the evening before. Following dosing, subjects will

fast for a period of 4 hours until lunch (for the MD cohorts, fasting after dosing will occur on Days 1 and 15 only; on all other dosing days in the MD cohorts, subjects should consume a non-standardized breakfast approximately 1 hour after dosing). For BID dosing, if studied, subjects will be fasted 1 hour before and after the evening dose. During fasting, no fluids are allowed except for water; however, water is not allowed from 2 hours predose until 1 hour postdose (apart from the water taken with the dose).

6.3.2. Caffeine, Alcohol, and Tobacco

Caffeine—Subjects should not be allowed caffeine consumption for 48 hours prior to all study visits and during CRU stays. At other times during the outpatient period, subjects will be allowed to maintain their regular caffeine consumption.

Alcohol—Alcohol consumption is not allowed from 48 hours prior to all study visits and during CRU stays. At all other times, alcohol consumption should be limited to no more than 2 units per day (1 unit = 12 ounces or 360 mL of beer, 5 ounces or 150 mL of wine, and 1.5 ounces or 45 mL of distilled spirits).

Tobacco—Subjects will be asked to refrain from smoking for approximately 48 hours prior to CRU admission and during CRU stays. During the follow-up period, subjects will be asked to refrain from smoking for 2 hours prior to study visits.

6.3.3. Activity

No strenuous exercise will be allowed for 48 hours prior to admission and during the study.

6.4. Screen Failures

Individuals who do not meet the criteria for participation in this study (screen failure) may be re-screened. Individuals may be re-screened once with Lilly clinical pharmacologist's approval. The interval between re-screenings should be at least 2 weeks. Each time re-screening is performed, the individual must sign a new informed consent form (ICF) and will be assigned a new identification number.

7. Treatment

7.1. Treatment Administered

This study involves a numerical comparison of LY3337641 (30 mg QD in MD cohorts and 5, 80, and 160 mg in SD cohorts) with placebo, when administered orally. The study drug is supplied as tablets containing 5 or 20 mg of LY3337641 with matching placebo tablets (Table JPDB.2).

LY3337641 and placebo will be administered orally with approximately 200 mL of room temperature water in the morning of each dosing day with the subject in a sitting position. Subjects will not be allowed to lie supine for 2 hours after dosing, unless clinically indicated or as needed for study procedures.

Table JPDB.2. Treatment Administered

| Cohort | Dose | Number of Tablets |
|----------|------------------|------------------------------------------------------|
| Cohort 1 | LY 30 mg QD | 1 x 20-mg LY tablet 2 x 5-mg LY tablets |
| | Placebo 30 mg QD | 1 x 20-mg placebo tablet 2 x 5-mg placebo tablets |
| Cohort 2 | LY 80 mg | 4 x 20-mg LY tablets |
| | Placebo 80 mg | 4 x 20-mg placebo tablets |
| Cohort 3 | LY 5 mg | 1 x 5-mg LY tablet |
| | Placebo 5 mg | 1 x 5-mg placebo tablet |
| Cohort 4 | LY 160 mg | 8 x 20-mg LY tablets |
| | Placebo 160 mg | 8 x 20-mg placebo tablets |

Abbreviations: LY = LY3337641; QD = once daily.

The investigator or designee is responsible for:

- explaining the correct use of the IP to the subject,
- verifying that instructions are followed properly,
- maintaining accurate records of IP dispensing and collection,
- and returning all unused medication to Lilly or its designee at the end of the study.

Note: In some cases, sites may destroy the material if, during the investigative site selection, the evaluator has verified and documented that the site has appropriate facilities and written procedures to dispose of clinical trial materials.

7.1.1. Packaging and Labeling

IP will be supplied by the sponsor in accordance with current good manufacturing practices. The material will be labeled with a unique identifier for drug accountability. Clinical trial materials will be labeled according to the country's regulatory requirements and will be labeled with the identity of the material contained in the package.

The study drug will be supplied as tablets containing 5 or 20 mg of LY3337641 with matching placebo tablets. The LY3337641 5-mg tablets and corresponding 5-mg matched placebo are identical in appearance, and the LY3337641 20-mg tablets and corresponding 20-mg matched placebo are identical in appearance. However, the 5 - and 20-mg tablets are not identical in appearance.

Packaging will be as follows:

5 mg LY3337641 blister card—9 tablets

Placebo to match 5 mg LY3337641 blister card—9 tablets

20 mg LY3337641 blister card—9 tablets

Placebo to match 20 mg LY3337641 blister card—9 tablets

7.2. Method of Treatment Assignment

Randomization tables for allocation of LY3337641 or placebo will be prepared by the statistician for the study and provided to the site pharmacists involved in dose preparation. The allocation and dispensing of the IP will be fully documented and verified by a second person. Detailed records of the amounts of the IP received, dispensed, and remaining at the end of the study will be maintained by the site pharmacist.

7.2.1. Selection and Timing of Doses

SDs will be administered in the morning. For the QD cohort(s), doses will be administered at approximately the same time in the morning on each day for each subject. If the BID regimen is tested in Cohort 5, the dose will be administered in the morning and the evening. The evening dose should be taken 12 hours apart from the morning dose. On Day 15, only the morning dose will be administered.

Meal conditions are discussed in Section 6.3.1. The actual time of all dose administrations will be recorded in the subject's electronic case report form (eCRF).

7.3. Blinding

Blinding will be maintained throughout the conduct of the trial until all data are cleaned to an acceptable level of quality and locked. The details are included in the Blinding/Unblinding Plan ([Appendix 6](#)).

The site pharmacist will be responsible for dispensing the IP to the subjects in a blinded manner. The investigator and subjects should remain blinded to study treatment within each cohort throughout the conduct of the study.

If a subject's study treatment assignment is unblinded, the subject must be discontinued from the study, unless the investigator obtains specific approval from a Lilly clinical pharmacologist or clinical research physician or for the study participant to continue in the study.

In case of an emergency, the investigator has the sole responsibility for determining if unblinding of a subject's treatment assignment is warranted for medical management of the event. Subject's safety must always be the first consideration in making such a determination. If the investigator decides that unblinding is warranted, the investigator should make every effort to contact the Lilly clinical pharmacologist or clinical research physician prior to unblinding a study subject's treatment assignment, unless this could delay emergency treatment of the subject. If a study subject's treatment assignment is unblinded, Lilly must be notified immediately.

7.4. Dose Modification

7.4.1. Dose Escalation

All doses in this study have been previously tested and shown to be well tolerated in Study JPDD. However, Japanese subjects have not received LY3337641 previously. The dose escalation decision will be made based on the safety data from both Japanese and Caucasian subjects up to Day 3 (48 hours postdose) of 80-mg SD administration (Cohort 2) to proceed to the 160 mg SD cohort (Cohort 4).

Safety data for the 80-mg SD will be the primary criteria for dose escalation to the 160-mg SD. In addition, if available at the time of dose escalation decision, PK (C_{max} , AUC, and clearance) results may be used as supporting data for dose escalation, but such data are not required. No dose escalation can occur without prior discussion and agreement between the investigator and the Lilly clinical pharmacologist or clinical research physician.

Safety data, in particular AEs, SAEs, and adverse laboratory abnormalities, will be independently assessed by the investigator and will be considered related to the IP, unless there is clear evidence that the event is not related.

After review of these data, an agreement on the appropriate dose escalation will be made by the investigator and sponsor for the 160-mg SD cohort. The magnitude of the dose escalation may be reduced following data review, but the highest SD will not exceed 160 mg.

If any of the following scenarios occur, dosing at the current level and further dose escalation will be stopped until the safety data can be reviewed:

- 1) 1 or more subjects experience an SAE
- 2) 2 or more subjects experience a clinically significant event that is related to LY3337641 administration
- 3) greater than 3 subjects at 1 dose level experience moderate treatment-related AEs that impair normal activities

After the safety review is completed, if Cohort 2 dosing has not been completed, dosing may resume if agreed upon by the investigator and sponsor. Once all data from Cohort 2 has been

obtained, an agreement on the appropriate dose escalation will be made by the investigator and sponsor for the 160-mg SD cohort or a lower dose.

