8.1. Discontinuation from Study Treatment

Discontinuation of the IP for abnormal liver tests **should be considered** by the investigator when a subject meets one of the following conditions after consultation with the Lilly-designated medical monitor:

- Alanine aminotransferase (ALT) or aspartate aminotransferase (AST) >5X upper limit of normal (ULN)
- ALT or AST >3X ULN along with one of the following criteria
 - sustained for more than 2 weeks or
 - total bilirubin level (TBL) >2X ULN or
 - prothrombin time >1.5X ULN or
 - the appearance of fatigue, nausea, vomiting, right upper-quadrant pain or tenderness, fever, rash, and/or eosinophilia (>5%)
- Alkaline phosphatase (ALP) >3X ULN
- ALP>2.5X ULN and TBL >2X ULN
- ALP>2.5 ULN with the appearance of fatigue, nausea, vomiting, right quadrant pain or tenderness, fever, rash, and/or eosinophilia (>5%)

In addition, subjects will be discontinued from the IP in the following circumstances:

- The investigator decides that the subject should be discontinued from the IP
- The subject requests to be discontinued from the IP
- Subject experiences an SAE or clinically significant event that is related to LY3337641 administration, or
- Subject experiences moderate treatment-related AEs that impair normal activities

When this situation arises, the investigator should inform a Lilly clinical pharmacologist or clinical research physician.

When subjects discontinue the IP early, procedures to be performed will be discussed between the investigator and the Lilly clinical pharmacologist or clinical research physician.

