9.2.1. Serious Adverse Events

An SAE is any AE from this study that results in one of the following:

- death
- initial or prolonged inpatient hospitalization
- a life-threatening experience (that is, immediate risk of dying)
- persistent or significant disability/incapacity
- congenital anomaly/birth defect
- events considered significant by the investigator based upon appropriate medical judgment

Study site personnel must alert Lilly, or its designee, of any SAE within 24 hours of investigator awareness of the event via a sponsor-approved method. If alerts are issued via telephone, they are to be immediately followed with official notification on study-specific SAE forms. This 24-hour notification requirement refers to the initial SAE information and all follow-up SAE information.

Pregnancy (maternal or paternal exposure to IP) does not meet the definition of an AE. However, to fulfill regulatory requirements any pregnancy should be reported following the SAE process to collect data on the outcome for both mother and fetus.

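### Stop criterion 3 (Protocol 7.4.1) counts only moderate related AEs, so three moderate events plus one severe, non-serious event can miss the pause (minor wording fix)

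*Protocol*

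**What the plan says.** Protocol 7.4.1 lists three triggers. Any one of them stops dosing at the current level and further escalation until the safety data have been reviewed:

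- Criterion 1: "1 or more subjects experience an SAE".
- Criterion 2: "2 or more subjects experience a clinically significant event that is related to LY3337641 administration".
- Criterion 3: "greater than 3 subjects at 1 dose level experience moderate treatment-related AEs that impair normal activities".

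Criterion 3 is limited to one dose level; criterion 2 is not. Neither document defines a clinically significant event or ties it to a severity grade. The same section makes relatedness the default: safety findings "will be considered related to the IP, unless there is clear evidence that the event is not related".

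The SAE definition in Protocol 9.2.1 ends with a judgment item, "events considered significant by the investigator based upon appropriate medical judgment", so the investigator can make a severe event serious by that route.

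Protocol 8.1 uses similar terms for the individual subject. IP is discontinued if "Subject experiences an SAE or clinically significant event that is related to LY3337641 administration", and also if "Subject experiences moderate treatment-related AEs that impair normal activities". The second of these again names only moderate events.

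**The concern.** A stop rule should respond at least as strongly to a worse set of events. Criterion 3 as worded need not. A related AE that is severe from onset and not serious is not a moderate AE, so it adds nothing to the count of more than three. It can trigger a pause only through criterion 1 or criterion 2, and both then depend on how the investigator labels the event. Criterion 2 also needs a second subject.

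With four subjects affected at one dose level, four moderate events therefore force a pause under criterion 3. Replacing one of them with a more severe event can remove it. What is at stake is whether the remaining dosing at that level is paused for review. No endpoint, analysis population or planned analysis is touched.

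**Working it through.** The plan gives no operating characteristics for the stop rule and does not base the sample size on power, so there is no figure to reproduce. The check is an enumeration.

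**Inputs.** A single-dose cohort has 8 subjects, 6 of them on LY3337641 (Protocol 5.1). Both numbers are used: the investigator is blinded and events count as related by default, so events in placebo subjects may be counted. The thresholds come from 7.4.1: at least 1 subject (criterion 1), at least 2 (criterion 2), and more than 3, that is at least 4, at one dose level (criterion 3).

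**Notation.** All events are related and impair normal activities.
- m = subjects at the dose level whose AE is moderate and not judged clinically significant.
- s = subjects at that level whose AE is severe from onset and meets none of the specific outcome items of the SAE definition.
- x = other subjects, at any dose level, with a clinically significant related event.

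Each subject is counted once.

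**Rules, with severe events judged clinically significant but not SAEs.**
- As written: pause if m ≥ 4 or s + x ≥ 2.
- Amended: pause if m + s ≥ 4 or s + x ≥ 2.

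**Step 1: combinations with at least four affected (m + s ≥ 4).** A total of k affected subjects can be split in k + 1 ways.
- 6 subjects: 5 + 6 + 7 = 18.
- 8 subjects: 5 + 6 + 7 + 8 + 9 = 35.

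**Step 2: x = 0.** The written rule misses a combination only if m ≤ 3 and s ≤ 1 while m + s ≥ 4. The only solution is m = 3, s = 1. That is 1 of 18 and 1 of 35. With exactly four affected:

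| m | s | As written | Amended |
|---|---|---|---|
| 4 | 0 | pause (criterion 3) | pause |
| 3 | 1 | no pause | pause |
| 2 | 2 | pause (criterion 2) | pause |
| 1 | 3 | pause (criterion 2) | pause |
| 0 | 4 | pause (criterion 2) | pause |

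**Step 3: x ≥ 1.** With s = 1, s + x ≥ 2 and criterion 2 applies. Nothing is missed.

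**Step 4: the severe event is judged an SAE under 9.2.1.** Criterion 1 applies at one subject. Nothing is missed.

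**Step 5: the severe event began as moderate, or the subject also had a moderate related AE that impaired activities.** That subject has experienced a moderate AE and counts under criterion 3, so the tally is four. Nothing is missed.

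**Step 6: Protocol 8.1.** One SAE or clinically significant related event already discontinues the subject, so on the labelling in Step 2 the missing *or worse* changes nothing there. In the single-dose cohorts no later dose remains to withhold from that subject.

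No probability is attached. The documents give no AE rates. A calculation on 6 or 8 subjects would also describe a fully dosed cohort, in which no dosing is left to pause.

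**The case against.** The strongest reply is that the three criteria form a ladder. SAEs stop at one subject, clinically significant events at two and moderate events at four, and severe events belong on the second rung. This is a fair reading, but it does not close the gap: the rungs are not added together, so one severe event stays below the threshold of two and is not carried down to the count of four.

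A second reply is that most readers would take moderate to mean at least moderate. If so, the amendment writes down what is meant. A stop rule should not depend on that.

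A third reply is that other safeguards exist, and this mostly stands. Cohort 4 starts only after the safety assessment of Cohort 2 up to Day 3, and escalation needs agreement between the investigator and the sponsor's physician or pharmacologist (5.1, 7.4.1). The sponsor's pharmacologist is unblinded and monitors safety throughout (9.4.5, Appendix 6). The protocol also states "All doses in this study have been previously tested and shown to be well tolerated in Study JPDD", although it adds that Japanese subjects have not been exposed before. What these safeguards do not fully replace is the automatic pause of dosing at the current level. How much dosing would be left to pause in a single-dose cohort is unknown, because the public text gives no dosing order within a cohort.

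The absence of a dose-level limit in criterion 2 also stands. Cohorts 1, 2 and 3 may run in parallel, so one clinically significant related event elsewhere closes the gap.

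**Conclusion.** The point holds as a minor wording error. Criterion 3, read literally, misses three moderate plus one severe-from-onset, non-serious related AE at one dose level. This requires that the severe event is judged clinically significant but not an SAE, and that no other subject has had a clinically significant related event. It is the only combination missed under those conditions. The consequence is limited to pausing the remaining dosing at that level.

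Three stronger readings are tempting, and the documents do not support them.

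- A reader might infer that severe events fall outside the stop rule altogether. If a severe related event were judged neither serious nor clinically significant, the written rule would miss every combination with m ≤ 3: 12 of the 18, or 20 of the 35. Nothing in the documents suggests that an investigator would label such events that way.
- A reader might infer that escalation to 160 mg could go ahead unchecked. It cannot: safety review and joint agreement are required whether or not a criterion is met.
- A reader might infer that 8.1 leaves a subject with a severe event on treatment. One SAE or clinically significant related event is already enough to discontinue.

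**What to change.** In criterion 3 of Protocol 7.4.1, replace *moderate* with *moderate or worse* and state that each subject is counted once. Leave the thresholds and the actions as they are. The same change to the matching bullet in 8.1 is optional, for consistency only.

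The change needs no new data and alters no analysis. The downside is an occasional extra pause for safety review. Where severe related events are already judged clinically significant, the only pause added is the three-plus-one case with no such event in another subject. Where they are judged SAEs, none is added.
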